Subjects will receive a significant amount of attention from medical professionals during the course of this investigation. They will be undergoing cardiac evaluations at frequent intervals. Extra attention will be devoted to ensuring that subjects are receiving the proper types and doses of medications at the proper time. Many studies have shown that patients benefit significantly in how they feel as a result of this type of increased medical surveillance, independent of any benefits that might be provided by the experimental treatment.

F. Description of and justification for the CCM dosage.

CCM signals are non-excitatory electrical signals delivered to the heart muscle in the left ventricle through commercially available implanted pacemaker leads. CCM signals resemble pacing signals in that they are characterized by a delay, duration and amplitude. Compared to pacing signals, CCM signals are multiphasic, are of wider pulse duration and are higher in amplitude. In this study, the signals will consist of two biphasic pulses ~10 ms in duration (total duration ~20 ms) with a maximum voltage of 7.5 V, unless the subject experiences a side effect (e.g., muscular stimulation, sensation), in which case the voltage may be decreased. The "dose" of CCM signals is determined primarily by the number of hours per day that the signal is delivered. The FIX-HF-5 Phase I and Phase II studies, FIX-HF-5B and FIX-HF-5C studies, and the FIX-HF-5C2 study have all utilized a CCM dose of 5 hour/day signal delivery paradigm. This has been clinically acceptable and for consistency, the present study shall

continue to use the 5 hour/day dose. All subjects shall receive five non-contiguous one-hour periods of CCM signal application per day, with a schedule of one hour ON and three hours 48 minutes OFF.

G. Statement of Compliance

This clinical trial will be conducted in compliance with the protocol, GCP and other region-specific applicable regulatory requirements.

H. Description of the population to be studied

Subjects entered into this study will be representative of the patient population with stable, systolic left ventricular dysfunction and moderate-to-severe symptomatic heart failure despite appropriate medical therapy. The population is generally characterized by NYHA Class III and IV symptoms and having a left ejection fraction measuring between 25 and 45% (inclusive).

II. STUDY OBJECTIVES

The primary objectives of this protocol include the following:

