1. Allow ongoing access to treatment of patients suffering from moderate to severe heart failure at selected investigational sites until the PMA order has been issued by the FDA for the OPTIMIZER System.
2. Evaluate quality life, as assessed by the Kansas City Cardiomyopathy Questionnaire (KCCQ).
3. Evaluate safety in the Continued Access study, and further into the post-approval study, by comparing the observed mortality rate to the predicted probability of mortality derived by the Seattle Heart Failure Model (SHFM) and the Meta-Analysis Global Group in Chronic Heart Failure (MAGGIC).

III. STUDY DESIGN

This is a multicenter, prospective, single-arm Continued Access study of the Optimizer Smart System with CCM therapy. All subjects will be followed until the PMA order has been issued by the FDA. The protocol is designed to collect adverse safety events, quality of life data and data needed for comparison with long term mortality prediction models.

A. Description of the study procedures and stages

The study will include baseline eligibility tests and assessments followed by implantation of the OPTIMIZER Smart device in eligible subjects. All subjects will be followed until the PMA order has been issued by the FDA. Additional follow-up may be required during the post market period for a minimum of 3 total follow-up years. Evaluation of subjects will be documented on electronic case report forms and will include the tests and procedures listed in

Table 1.

Table 1. Schedule of Tests and Assessments

Tests and Assessments	Screening /Baseline	OPTIMIZER Implant	2 Weeks ± 7 days	30-40 Days	6 Mo ± 1 mo	1 Year ± 1 mo	Every 6 months †
Informed Consent	X						
Medical History and Risk Factors	X						
Blood Testing*	X						
Follow-up Assessment			X		X		
NYHA Class	X				X		
Medications	X				X		
Physical Examination	X				X		
12-Lead EKG**	X						
24-Hour Holter Monitor**	X						
Echocardiogram**	X						
KCCQ	X				X	X	
Eligibility determination	X						
OPTIMIZER Smart System Implant		X					
Chest X-ray (prior to hospital discharge)		X					
OPTIMIZER Device Interrogation / Programming		X	X		X	X	X
Safety Reporting		X	X	X	X	X	X

* Baseline blood testing (Creatinine, Hgb, Lymphocyte %, Uric Acid, Total Cholesterol and Sodium) performed within 30 days before informed consent may be used for baseline testing.

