** 24-Hour Holter Monitor, 12-Lead EKG and Echocardiogram test results obtained within 60 days before informed consent and performed in accordance with the protocol, may be used for eligibility determination.

† Visits shall continue every 6 months until the PMA Supplement order has been issued by the FDA.

B. Anticipated Number of Sites and Subject Recruitment Rate

Up to 350 eligible subjects may be enrolled (providing consent and implanted). Eligible study participants may be enrolled from a maximum of 40 study sites in the United States.

C. Expected duration of subject participation

All eligible subjects will be asked to participate in the study until the PMA order has been issued by the FDA. Subjects can expect to participate for up to 2 years. The sequence and duration of specific study periods are described in **Table 1**.

D. Description of the Study “stopping rules” or “discontinuation criteria”

There shall be no stopping rules or discontinuation criteria. Enrollment into the Continued Access study shall end upon the issue of the PMA order by the FDA.

E. Accountability procedures for investigational products.

Clinical investigators will be trained in the importance of investigational products accountability. Impulse Dynamics will deliver OPTIMIZER Smart System related hardware to each enrolling clinical site, including the OPTIMIZER Smart IPGs, Chargers and an OMNI Smart Programmer. IPGs are generally not stored with the site inventory but rather carried in for each implant case by the engineer.

In accordance with 21 CFR 812.140, the clinical investigator is responsible for maintaining records of receipt, use or disposition of the investigational devices including:

- the type and quantity of the device, dates of receipt, and batch numbers or code marks
- names of all persons who received, used, or disposed of each device
- the number of units of the device returned to the sponsor, repaired, or otherwise disposed of, and the reason(s) therefore.

The IDE Device Accountability Log shall be maintained and updated throughout the study.

In accordance with 21§812.110, upon completion or termination of the clinical study or the investigator's part of the study or at Impulse Dynamic's request, the investigator shall return any remaining investigational product.

F. Data to be recorded directly onto CRFs and considered to be source data.

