Serious Adverse Device Events/Effects (SADEs): All SADEs will be reported for as long as the subject is active in the study. An Optimizer device- or Optimizer procedure-related AE shall be classified as “serious” if there is an untoward medical occurrence that results in death, is life-threatening, requires inpatient hospitalization, prolongation of existing hospitalization or invasive treatment, results in persistent or significant disability/incapacity or is a congenital anomaly/birth defect.

- The term “disability” in the definition above refers to substantial disruption of the subject’s ability to conduct normal life functions.
- The term "life-threatening" in the definition above refers to an event that places the patient, in the view of the investigator, at immediate risk of death from the event as it occurred; it does not refer to an event that hypothetically might have caused death if it were more severe or left untreated.

Impulse Dynamics will review serious adverse device events and deaths to determine whether an unanticipated adverse device effect may have occurred.

3. Unanticipated Adverse Device Effect (UADE)

In accordance with CFR 21 § 812.3(s), a UADE is any serious adverse effect on health or safety or any life-threatening problem or death caused by, or associated with, a device, if that effect, problem, or death was not previously identified in nature, severity, or degree of incidence in the investigational plan or application; or any other unanticipated serious problem associated with a device that relates to the rights, safety, or welfare of subjects.

4. Mortality

All deaths, regardless of whether it is related to the study device, study procedure, or not, shall be reported.

B. Procedures for reporting UADEs

1. Investigator Reporting Obligations

The Investigator shall report all safety events defined in section VI.A of the current protocol to Impulse Dynamics and to the reviewing IRB (as/if required according to IRB policy). Serious adverse device events (SADEs) must be reported to Impulse Dynamics within 1 business day after the Investigator learns of the event.

According to 812.150(a), the Investigator is required to submit a report of any UADE occurring during the study to Impulse Dynamics and to the reviewing IRB as soon as possible, but in no event later than 10 working days after he/she first learns of the effect.

2. Sponsor Reporting Obligations

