In accordance with CFR 21 § 812.46, Impulse Dynamics will immediately conduct an evaluation of any UADE. If Impulse Dynamics determines that a UADE presents an unreasonable risk to subjects, it will terminate all investigations or parts of the investigations presenting that risk as soon as possible. Termination will occur no later than 5 working days after Impulse Dynamics makes this determination and no later than 15 working days after Impulse Dynamics first received notice of the effect.

VII. ASSESSMENT OF EFFECTIVENESS

Change in quality of life, as assessed by the Kansas City Cardiomyopathy Questionnaire.

VIII. ASSESSMENT OF SAFETY

Safety will be assessed by comparing the prevalence of mortality observed in the Continued Access Study (CAS) to the predicted probability of mortality derived from two validated heart failure models [MAGGIC (Meta-Analysis Global Group in Chronic Heart Failure) and SHFM (Seattle Heart Failure Model)]. The objective is to show that the observed prevalence of mortality is not worse than the derived predicted probability of mortality. Two pairwise comparisons (CAS vs. MAGGIC, CAS vs. SHFM) will be performed at 1 year and 3 years. Observed statistical differences will be noted if the two-sided p-value is less than 0.05.

A. Seattle Heart Failure Model (SHFM)

Specific baseline data will be collected in order to predict survival based on the SHFM. Computation of the SHFM score is done with 14 continuous variables and 10 categorical values; a web-based calculator is available to perform the calculation (<http://www.SeattleHeartFailureModel.org>).

B. Meta-Analysis Global Group in Chronic Heart Failure (MAGGIC)

Specific baseline data will be collected in order to predict survival based on the MAGGIC Prognostic Heart Failure Survival Model. The model identifies 13 independent predictors that should be routinely available although provisions have been made by the website (www.heartfailurerisk.org) for one or two variables to be unknown for an individual.

C. Censored and Missing Data

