In the SHFM and MAGGIC analyses above, subjects receiving an LVAD or heart transplant, cases of a device explants, and cases of a decision to permanently stop the therapy will be censored at the time of that change of therapy. These will be documented in the CRF, and will not be counted as an event. In any case of interim analysis, for the purpose of the Kaplan-Meier analysis, unless known otherwise, all cases that are under ongoing routine follow-up that have not yet completed the 3 years period shall be assumed to be alive and treated until the date of analysis.

Missing values may be overcome using imputation by the mean value of the cohort, or default values of the model for similar cohorts.

IX. OTHER ASSESSMENTS

Change in heart failure symptoms will be assessed using the NYHA classification assigned by a site clinician according to their standard clinical practice.

X. DIRECT ACCESS TO SOURCE/DATA DOCUMENTS

The investigators and institutions will permit trial-related monitoring, audits, IRB review, and regulatory inspections, providing direct access to source/data and regulatory documents.

XI. QUALITY CONTROL AND QUALITY ASSURANCE

Quality control and quality assurance is the responsibility of the Investigator and designated study staff. Impulse Dynamics clinical representatives will provide training and support to ensure that data quality is optimal (accurate, valid, reliable, complete and reported in a timely manner). Data will be monitored in accordance with Impulse Dynamic's Monitoring procedures. Data used for publication will not identify the subjects; publications will be generated in accordance with Impulse Dynamic's publication policy.

XII. ETHICS

Heart failure is a prevalent health problem throughout the world. Development of therapies to improve heart function to relieve symptoms, reduce hospitalizations and improve survival is a high priority in cardiovascular medicine.

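### The mortality objective is to show observed deaths are not worse than predicted, but the only stated criterion is a two-sided difference test, which cannot show that when mortality is close to prediction

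*Protocol*

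**What the plan says.** Section II introduces its list with "The primary objectives of this protocol include the following". The third item evaluates safety by "comparing the observed mortality rate to the predicted probability of mortality" from the SHFM and MAGGIC models.

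Section VIII goes further: "The objective is to show that the observed prevalence of mortality is not worse than the derived predicted probability of mortality". It plans a comparison with each model at 1 year and at 3 years, so four comparisons in all. The criterion is: "Observed statistical differences will be noted if the two-sided p-value is less than 0.05".

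Section VIII.C adds handling rules only. Subjects with an LVAD, a transplant, an explant or permanently stopped therapy "will be censored at the time of that change of therapy". At an interim analysis, subjects still in routine follow-up are taken as alive and treated "for the purpose of the Kaplan-Meier analysis". Missing model inputs may be imputed. No margin, confidence bound or rule for concluding not worse appears in these sections.

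On size, Section III.B says "Up to 350 eligible subjects may be enrolled". This is a ceiling; no minimum is given.

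**The concern.** Showing that mortality is not worse than a reference is a non-inferiority type of aim. It is met by ruling out a material excess, normally with an upper confidence limit. A two-sided difference test answers another question. It can establish that mortality differs from prediction, in either direction, but failing to reject equality does not show that an excess is absent. The smaller the cohort, the easier it is to obtain p≥0.05.

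The comparison belongs to a listed primary objective of a single-arm study, and it is the protocol's only statistical comparison of mortality with a reference. Under Section VI.A.2 the sponsor "will review serious adverse device events and deaths to determine whether an unanticipated adverse device effect may have occurred", but that is a case-by-case review and does not test cohort mortality. If observed mortality lands near prediction, the stated conclusion could be reached only by treating non-significance as proof, when the data may still be compatible with a material excess.

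**Working it through.** The protocol gives no power, event count or margin for this comparison, so there is no figure of its own to reproduce. The check is how the stated criterion behaves.

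**Inputs**
- N=350: the Section III.B ceiling.
- Two-sided 0.05: Section VIII, applied here as 2.5% in each tail.
- Predicted 1-year mortality p0: not given for this cohort. Assumed 10% and 20%. The 20% matches the approximate annual Class III rate in Section I.E.1.a, which is a background figure and not a model prediction.
- Simplifications: prediction treated as a known constant, no censoring, one model.

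**1-year test.** With deaths X ~ Binomial(350, p0), the result is significantly low if P(X≤x)≤0.025 and significantly high if P(X≥x)≤0.025.
- p0=10%: expected 350×0.10=35 deaths; significant at ≤23 or ≥47.
- p0=20%: expected 350×0.20=70 deaths; significant at ≤55 or ≥86.

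Setting the true probability to ratio×p0:

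| True ratio | Outcome | p0=10% | p0=20% |
|---|---|---|---|
| 0.75 | significantly low | 30% | 68% |
| 0.90 | significantly low | 6% | 15% |
| 1.00 | significantly low | 1.6% | 2.4% |
| 1.00 | non-significant | 96.0% | 95.5% |
| 1.25 | excess not flagged | 68% | 41% |
| 1.50 | excess not flagged | 18.5% | 1% |

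With an assumed N=200, the upper cut-offs are 30 and 52 deaths, and a 1.25-fold excess goes unflagged 83% / 60% of the time.

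**Largest non-significant counts at N=350** (p is twice the upper tail; Clopper-Pearson limits divided by p0)
- p0=10%: 46 deaths, ratio 46/35=1.31, p=0.069, 95% CI 0.98 to 1.71.
- p0=20%: 85 deaths, ratio 85/70=1.21, p=0.057, 95% CI 0.99 to 1.46.

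Neither count is flagged, yet the intervals allow excesses of about 70% and 45%.

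**1 and 3 years together.** Assume constant hazard and complete 3-year follow-up. Predicted 3-year mortality is 1−0.9³=0.271 (significant at ≤78 or ≥112 deaths) and 1−0.8³=0.488 (≤151 or ≥190). With hazard ratio h, the true 1-year probability is 1−(1−p0)^h. Joint probabilities come from summing over 1-year deaths, then binomial deaths in years 2 and 3 among survivors:
- h=1.00: both looks non-significant 92% / 92%.
- h=1.25: excess not flagged at either look 34% / 14%.
- h=1.50: excess not flagged at either look 0.9% / 0.01%.
- h=0.75: significantly low at 3 years 73% / 93%.

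**The case against.** The strongest reply is that the protocol never says p≥0.05 counts as success. It says differences will be noted, which is reporting language, and the SAP, which is not shown, could add a margin or a one-sided bound without contradicting it. This is right as far as it goes: the misreading is a risk and not a stated rule, and the analysis details may properly sit in an SAP. But the protocol itself fixes both the aim and the criterion, and the two do not match. An SAP that added a margin would still have to be reconciled with Section VIII.

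Second, the route is not empty. If the true hazard were 0.75 of prediction, full 3-year follow-up would give a significantly low result 73% / 93% of the time. That stands, but it helps only when mortality is well below prediction.

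Third, the percentages rest on assumed rates and the enrolment ceiling, and large excesses are usually caught at full size. Both points are correct, so the figures illustrate the problem and do not measure an error in this trial.

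Fourth, no enrolment or treatment decision depends on the p-value: Section III.D has no stopping rules, and deaths are also reviewed individually. That limits the consequence to what the study may conclude about mortality, which is still a listed primary objective.

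**Conclusion.** The concern holds and should be fixed. Section VIII promises a conclusion that its stated criterion can deliver only if mortality is significantly below prediction. When true mortality equals prediction, the criterion leaves the objective unanswered about 95% to 96% of the time at 1 year, and 92% of the time across both looks. At full enrolment, large excesses are usually detected but moderate ones often are not: a 1.25-fold excess is missed 68% / 41% of the time at 1 year, and a 1.25-fold hazard escapes both looks 34% / 14% of the time. These figures assume 350 subjects, predicted 1-year mortality of 10% / 20% treated as fixed, one model and no censoring; the two-look figures add constant hazard and complete 3-year follow-up. Smaller cohorts miss more. The mismatch itself needs none of these assumptions.

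**What to change.** **Main option.** Reword the Section VIII aim as a comparison of observed with predicted mortality, in line with Section II. For each model, at 1 and 3 years, report Kaplan-Meier mortality under the Section VIII.C censoring, the cohort-mean predicted mortality at the same time, and their ratio with a 95% confidence interval (prediction treated as fixed). State that p≥0.05 will not be interpreted as not worse. This costs a few sentences and a confidence interval around an estimate the protocol already mentions, with no extra subjects or data. The study gives up not worse as a stated conclusion.

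**If the sponsor wants to keep the claim.** Fix and justify a margin before mortality data are examined, require the upper confidence limit to lie below it, and say whether both models and both time points must pass. This is a real trade-off. For one comparison at N=350, passing when the Clopper-Pearson upper limit is below margin×p0 (illustrative margins; p0=10% / 20%):

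| Margin (ratio) | Most deaths that pass | Pass if truth equals prediction | Pass if true ratio is 1.25 |
|---|---|---|---|
| 1.5 | 39 / 87 | 79% / 99% | 25% / 50% |
| 1.25 | 31 / 71 | 27% / 58% | 2% / 2% |

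With few deaths the claim may be out of reach: at an assumed N=100, 10% predicted and margin 1.5, at most 7 deaths pass, with probability 21% when truth equals prediction. Requiring both models and both time points lowers all these pass rates.

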Class III and IV heart failure patients are at risk for death from their underlying disease, with annual mortality rates ranging from ~20% for Class III patients to as high as ~75% for Class IV patients. With any invasive cardiovascular procedure in heart failure patients there may be added risk of death. Invasive aspects and the associated risks of the OPTIMIZER implant procedure and device system are described below. Additionally, there may be an increased risk of death associated with the application of cardiac contractility modulation therapy. Applying appropriate subject selection criteria, using meticulous techniques and providing attentive post-procedure care will minimize the risks associated with these procedures.

b. Risks of implantation of the OPTIMIZER Smart pulse generator

The risks associated with implantation of the OPTIMIZER Smart pulse generator are similar to those of implanting a permanent pacemaker, which are well characterized and include (but are not limited to) infection, bleeding, pneumothorax, myocardial perforation by the leads and pain at the incision site. Applying appropriate subject selection criteria, using meticulous surgical technique and providing careful post-operative care will minimize the risks associated with these procedures.

c. Arrhythmias and/or palpitations associated with CCM signal application

Arrhythmias may occur as a result of CCM signal application. Arrhythmias may include bradyarrhythmias or tachyarrhythmias as well as ventricular arrhythmias or supraventricular arrhythmias and may be associated with palpitations. These may include sinus bradycardia, complete heart block, junctional rhythm, asystole, sinus tachycardia, atrial fibrillation, atrial flutter, paroxysmal atrial tachycardia, multifocal atrial tachycardia, premature atrial contractions, premature ventricular contractions, nonsustained or sustained ventricular tachycardia, ventricular fibrillation, electromechanical dissociation, or cardiac arrest. Palpitations are commonly reported in patients with heart failure and may or may not be associated with arrhythmias. Safety algorithms intended to minimize the incidence of arrhythmias have been incorporated into the OPTIMIZER Smart System.

d. Myocardial damage

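### Censoring deaths after explant or permanent therapy stop takes them out of observed mortality, while the baseline prediction has no matching restriction

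*Protocol*

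**What the plan says.** Section II makes the comparison of observed with predicted mortality a primary objective. Section VIII sets the aim: "The objective is to show that the observed prevalence of mortality is not worse than the derived predicted probability of mortality". There are two pairwise comparisons, with MAGGIC and with SHFM, each at 1 and 3 years. A difference is noted at a two-sided p-value below 0.05.

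Section VIII.A gives the source of the prediction: "Specific baseline data will be collected in order to predict survival based on the SHFM". VIII.B says the same for MAGGIC. Neither restricts the prediction to subjects who keep the device or stay on therapy.

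Section VIII.C then governs the observed side. For explant and permanent therapy stop it says "cases of a device explants, and cases of a decision to permanently stop the therapy will be censored at the time of that change", and it adds "These will be documented in the CRF, and will not be counted as an event". LVAD and transplant are handled in the same way. An estimator is named only in the sentence about interim analyses, "for the purpose of the Kaplan-Meier analysis".

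Elsewhere, VI.A.4 requires every death to be reported whatever its cause, and IV.C promises good-faith efforts to establish the vital status of every implanted subject. Neither overrides the censoring rule, and the protocol describes no analysis that counts deaths after explant or therapy stop.

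**The concern.** The observed quantity is mortality while on therapy. The predicted quantity is mortality from baseline with no such condition. A death after explant or therapy stop is therefore removed from only one side.

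That is harmless to a Kaplan-Meier estimate only if leaving therapy is unrelated to prognosis. The protocol gives reasons to doubt this. Section I.E.1.n lists malfunction, infection and sepsis among the reasons a component may have to be removed, although noninvasive correction, repositioning and replacement are also possible. Section I.E.1.h describes ineffective therapy with worsening heart failure. A subject explanted for sepsis who dies soon afterwards would count as alive at explant in the only mortality comparison the protocol states.

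Other departures need not signal decline. Under IV.C a subject may withdraw at any time, and the device is then deactivated. VIII.C does not say whether that counts as a permanent stop.

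At stake is the chance that a real excess in mortality is noted. Safety reporting itself is not affected, since all deaths are still reported and reviewed.

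**Working it through.** The protocol gives no sample size, margin or event calculation for this comparison, so there is no figure to reproduce. The check asks how far censored mortality can lie from all-death mortality.

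**Inputs from the protocol.** Section I.E.1.a: "annual mortality rates ranging from ~20% for Class III patients to as high as ~75% for Class IV patients". The Class III figure of 20% a year is used. Maximum enrolment is 350 (III.B), the time points are 1 and 3 years, and the two-sided level is 0.05 (VIII).

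**Assumptions.** Departure hazard q of 0.01, 0.03, 0.05 or 0.10 a year; death hazard after departure k times the on-therapy hazard, with k from 0.5 to 4; an alternative annual mortality of 10%.

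**Model.** With constant hazards, d = -ln(0.8) = 0.2231 on therapy.

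- Alive on therapy at t: S1 = exp(-(d+q)t)
- Alive after departure: S2 = q[exp(-kdt) - exp(-(d+q)t)]/(d+q-kd)
- All-death mortality: 1 - S1 - S2
- Kaplan-Meier limit with censoring at departure: 1 - exp(-dt)
- Crude on-therapy deaths over all implanted: d/(d+q) × [1 - exp(-(d+q)t)]

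**Example: t = 3, q = 0.05, k = 2.** S1 = 0.441 and S2 = 0.052, so all-death mortality is 50.8%. The Kaplan-Meier limit is 1 - 0.8³ = 48.8%, which is 2.0 points too low. The crude proportion is 45.7%, which is 5.1 points too low. The crude proportion is also 3.1 points too low when k = 1 (45.7% against 48.8%), and it is low in every scenario run.

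**Kaplan-Meier minus all-death mortality at 3 years, 20% annual mortality (points):**

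| q per year | k=0.5 | k=1 | k=2 | k=3 | k=4 |
|---|---|---|---|---|---|
| 0.01 | +0.3 | 0 | -0.4 | -0.7 | -0.9 |
| 0.03 | +0.8 | 0 | -1.2 | -2.0 | -2.5 |
| 0.05 | +1.4 | 0 | -2.0 | -3.3 | -4.1 |
| 0.10 | +2.6 | 0 | -3.8 | -6.2 | -7.8 |

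At 1 year, with q from 0.03 to 0.10 and k from 2 to 4, the range is -0.3 to -2.1; with q = 0.01 it is -0.1 to -0.2. At 10% annual mortality, q from 0.03 to 0.10 and k from 2 to 4 give -0.1 to -1.2 at 1 year and -0.9 to -7.0 at 3 years.

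**Scale.** The 95% half-width with 350 subjects is 1.96√(0.2×0.8/350) = 4.2 points at 1 year and 1.96√(0.488×0.512/350) = 5.2 points at 3 years.

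**Chance of noting a real excess at 3 years.** Take the prediction as fixed at 48.8% and the true cumulative hazard as 1.25 times larger, so true mortality is 1 - 0.8^3.75 = 56.7%. For each scenario d is re-solved so that all-death mortality stays at 56.7%. With p the expected estimate and SE = √(p(1-p)/n), the chance is Φ((p - 0.488)/SE - 1.96). Counting all deaths with n = 350: SE = 0.0265, (0.567 - 0.488)/0.0265 = 2.98, and Φ(1.02) is about 85%.

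| Scenario | Expected estimate | n=350 | n=200 |
|---|---|---|---|
| All deaths counted | 56.7% | 85% | 61% |
| q=0.01, k=2 | 56.3% | 80% | 57% |
| q=0.03, k=2 | 55.5% | 71% | 48% |
| q=0.05, k=2 | 54.7% | 60% | 39% |
| q=0.05, k=3 | 53.5% | 42% | 26% |
| q=0.05, k=0.5 | 58.2% | 95% | not listed |

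A simulation of 20,000 runs using Kaplan-Meier and Greenwood standard errors, which includes the precision lost to censoring, gave 83, 79, 68, 56, 40 and 92% for the six rows at n = 350. With an unchanged hazard at q = 0.05 it gave 81%.

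**The case against.** The strongest reply is that VIII.C states an on-therapy analysis openly and in advance. That is a coherent quantity, and it is biased only when judged against all-death mortality. This is true as far as it goes. But sections II and VIII present the comparison as a safety assessment against a prediction with no therapy condition, and all-death mortality is the quantity that matches that prediction.

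The second reply is that the size is assumed. This stands. The -7.8 points need 10% departure a year and a 4-fold later hazard. About 19% of implanted subjects would then leave therapy alive by year 3 and die at about 59% a year. At 1-3% departure and a 2-fold hazard the 3-year shift is 0.4-1.2 points, below one standard error (about 2.7). At 1 year every scenario lies within sampling error.

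The 20% base may also be high. Section I.D.5 reports no deaths at 6 months among 49 Class III subjects in the feasibility study. At 20% a year the chance of that is 0.8^24.5, about 0.4%; at 10% it is about 8%. That study is small and selected. At 10% annual mortality the loss of power remains: with 350 subjects and a 1.25-fold excess, about 60% counting all deaths against 45% at 3% departure and a 2-fold hazard.

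The power figures are also illustrative in assuming 350 subjects followed for 3 years. III.C expects participation of up to 2 years, and III.A says only "Additional follow-up may be required during the post market period for a minimum of 3 total follow-up years".

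Finally, vital status after withdrawal may be incomplete, and deaths may be found more readily than survival is confirmed. Counting later deaths could then push the estimate up. This is a real but small drawback of the fix.

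**Conclusion.** The concern holds. The censoring rule is fixed in the protocol, acts on only one side of a primary safety comparison, and nothing else in the protocol restores the lost deaths. A downward bias is plausible, not proven. It needs a higher death hazard after explant or therapy stop, and its size depends on departure rates the protocol does not give.

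At 1 year the effect is small against sampling error. At 3 years it ranges from under 1 point at 1% annual departure to several points at 5-10%, and it can materially lower the chance of noting a real excess. If the observed figure is a crude proportion instead of a Kaplan-Meier estimate, it is low in all scenarios run. No direction is claimed for censoring at LVAD or transplant, because the protocol does not say how the models treated these.

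This should be fixed because the correction is cheap. It does not make the study unsound.

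**What to change.** Reword VIII.C as follows.

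- In the main 1- and 3-year comparisons, do not censor at explant or permanent therapy stop, including deactivation at withdrawal. Count every death after implant while vital status is known, and censor otherwise at the date of last known vital status.
- Keep the on-therapy version, censored at the change of therapy, as a labelled sensitivity analysis.
- Censoring at LVAD or transplant may stay in the main analysis, with a labelled sensitivity analysis that counts later deaths.
- State that the observed mortality in section VIII is the Kaplan-Meier estimate.
- Report how many subjects left therapy, and for how many of them vital status is known at each time point, so that uneven ascertainment can be seen.

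The cost is wording and one or two labelled analyses. No new kind of data is needed: deaths are reportable (VI.A.4), vital status is sought for every implanted subject (IV.C) and therapy changes go in the CRF (VIII.C). The drawbacks are a possibly higher observed mortality figure and reliance on good-faith follow-up after withdrawal.
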